during the call. Study staff will also use video whenever possible. The study staff will use the Zoom chat function or email to send the participant survey links and will verbally instruct them on how to complete the surveys, beginning with the consent survey. The oral consent form document will be embedded within the Qualtrics survey such that the participant can download the consent form document, or alternatively may be emailed to the participant. The study staff will ask the participant to read aloud the first part of the consent form in order to confirm that they were able to download the document and are able to read English fluently. Then the participant will be provided the opportunity to review the document and ask the study staff any questions they have about participation. This will be followed by a consent quiz administered via Qualtrics survey link. Participants will provide oral consent and answer all of the consent quiz questions correctly prior to proceeding with the remaining screening questionnaires. Following consent, participants will complete standardized medical/substance use history questionnaires as well as surveys to determine their caffeine/cigarette use, caffeine-related problems, and standardized assessments of anxiety, sleep, and gastrointestinal problems as outlined in Table 1. The participant will fill out the surveys via Qualtrics links, or the study staff will interview them and enter their responses on the study staff computers. Study staff will provide instructions to guide them through the assessment completions, review their responses on Qualtrics, and may ask follow-up questions if necessary, to supplement their survey responses. After determining eligibility, participants will be randomized to either the Immediate or Delayed treatment group using an urn randomization procedure accounting for caffeine consumption, age, and sex as was utilized in prior research in our laboratory (Evatt et al., 2016; Sweeney et al., 2019).

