Community Observer. During the screening or treatment visit, participants will be asked to provide the name and contact information (phone number and email address; email will be the preferred method of contact) for a family member, friend, roommate, or significant other for the purposes of online surveys about their caffeine use. The participant will be asked to confirm with their observer that the study team has permission to contact them. The observer will be contacted twice to complete a brief online survey regarding the participants' caffeine use. The first contact will occur soon after the participant has the *Treatment* visit. The second contact will occur near the time of the participant's *Week 7 follow-up* visit.

Treatment Televisit. Participants determined to be eligible following the screening televisit will be scheduled to complete the treatment televisit shortly after screening. For the immediate treatment group, the treatment the *Treatment* visit will generally occur within one week of the screening televisit. The delayed treatment group will have their *Treatment* visit scheduled for a date approximately 7 weeks after screening. During the *Treatment* televisit, study staff will provide the participants with a digital copy of the caffeine reduction treatment manual used in prior studies (Evatt et al., 2016; Sweeney et al., 2019). As in prior research (Sweeney et al., 2019), study staff will give a brief (i.e., generally less than five minutes) description of the manual and instructions on how to gradually reduce their caffeine consumption over a period of six weeks. Participants will also complete assessments to determine their caffeine consumption and cigarette use over the past 7 days as outlined in Table 1. Participants will also be provided with information about their follow-up visits and how to complete weekly surveys.

Weekly Surveys. At seven days following the treatment televisit, participants will receive a request to complete a survey via Qualtrics link sent via email/text. The survey will consist of standard assessments of anxiety, depressed mood, sleep problems, gastrointestinal problems, past week caffeine/cigarette intake, and problems related to caffeine as outlined in Table 1. They will receive a request to complete the same survey once per week (weeks 1-6) until the Week 7 follow-up televisit.

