5. Any medical condition that, in the opinion of the investigators, may interfere with or preclude completion of the study

6. Drugs/ Substances/ Devices

- a. The rationale for choosing the drug and dose or for choosing the device to be used.

There are no proposed drugs or devices in the proposed research study.

- b. Justification and safety information if FDA approved drugs will be administered for non-FDA approved indications or if doses or routes of administration or participant populations are changed.

N/A

- c. Justification and safety information if non-FDA approved drugs without an IND will be administered.

N/A

7. Study Statistics

- a. Primary outcome variable.

To determine to what extent participants will engage with a remote caffeine reduction intervention for caffeine-related problems and find it acceptable (*Primary objective*), we will calculate the percentage of completed assessments for each televisit (Treatment, 7 Week Follow-Up, 14 Week Follow-Up) among eligible participants, as well as self-reported agreement with the items on the treatment acceptability survey completed at the 7 Week Follow-Up televisit (e.g., “I read all or most of the Guide to Caffeine Reduction and Cessation,” “Overall, the guide was helpful during my attempt to reduce or quit caffeine.”)

- b. Secondary outcome variables.

To determine to what extent participants are successfully able to reduce their caffeine consumption following the remote intervention (*Secondary objective (a)*), we will assess caffeine consumption as determined by the caffeine surveys at 7-and 14-week post-treatment follow-ups and compare this with consumption at the screening and treatment televisits.

To determine to what extent participants report improvement in common caffeine-related problems (e.g., insomnia, anxiety, gastrointestinal distress) following the remote intervention (*Secondary objective (b)*), we will assess caffeine related problems, anxiety, sleep problems, and gastrointestinal distress via standardized measures (see Table 1) at 7 and 14 weeks post treatment follow-ups and compare this with scores on these assessments at the screening and treatment televisits.

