To determine whether participants randomized to the immediate intervention group show greater caffeine reductions or greater improvements in caffeine-related problems (*Secondary objective (c)*) at the 7-week follow-up relative to the delayed treatment group over the same time-period, we will compare all of the secondary outcome variables described above between the two treatment groups to compare our intervention relative to spontaneous reduction that may occur with the passage of time.

c. Statistical plan including sample size justification and interim data analysis.

Because the primary purpose of this study is to collect pilot and feasibility data rather than determine efficacy via randomized controlled trial, the statistical analysis will be primarily descriptive. Primary outcomes will be reported as the proportion of completed televisits among eligible participants as well as the mean and standard deviation agreement (visual analog scale) with items on the treatment acceptability survey. With respect to secondary outcomes, means and standard deviations for the standardized assessments in Table 1 will be calculated for screening, treatment, 7 Week Follow-Up and 14-Week Follow-Up visits, and we will also visually inspect individual subject data. With respect to comparisons between the immediate and delayed intervention group, we will use a mixed effects regression model with between-subjects factors of group, a within subjects factor of time, and a group x time interaction term. A power analysis indicates that with two groups, four measurements, an alpha of .05, a desired power of .95, correlation among repeated measures of .5, and conservatively estimating a small effect (e.g., partial eta squared = .02), a sample size of 100 will be sufficient to detect a treatment effect. Further, we will calculate Cohen's *d* and partial eta squared effect sizes using means and standard deviations for pre-and post-treatment for all secondary outcomes. These effect size calculations will be used to determine the necessary sample size for any future large-scale randomized controlled trials to assess clinical effects in different treatment populations. The desired sample size of 100 is also based on our laboratory's proven participant capacity for prior randomized clinical trials and long-term human laboratory studies (e.g., Evatt et al., 2016; Sweeney et al., 2017, Sweeney et al., 2019).

d. Early stopping rules.

8. Risks

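### The attendance part of the primary outcome is worded two ways with no stated split by randomised group, so loss during the delayed group's wait could be mixed with engagement with the intervention

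*Combined protocol and SAP*

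**What the plan says.** Section 2 sets the primary objective: how far participants engage with the remote intervention and find it acceptable. For engagement, section 7.a states: "we will calculate the percentage of completed assessments for each televisit (Treatment, 7 Week Follow-Up, 14 Week Follow-Up) among eligible participants". Section 7.c gives the reported measure as "the proportion of completed televisits among eligible participants". Both sections add a second component, agreement with the acceptability items collected at the Week 7 visit.

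The order of events is in section 4.a. Under Screening Televisit: "After determining eligibility, participants will be randomized to either the Immediate or Delayed treatment group". The method is an urn scheme that balances caffeine intake, age and sex. No allocation ratio is given. Under Treatment Televisit, the immediate group's Treatment "visit will generally occur within one week of the screening televisit", while the delayed group has its Treatment "visit scheduled for a date approximately 7 weeks after screening". The manual is handed over at that visit, and section 4.h says that the manual and the short instructions are the whole intervention. Week 7 and Week 14 are counted from the Treatment visit.

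The between-group comparison described in section 7.b is for the secondary outcomes. Section 4.g removes participants who do not comply, without saying whether they stay in the denominator. No target, expected rate or precision is given for engagement.

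**The concern.** Two things do not fit together. First, the unit differs between the two sections (assessment against visit), and 7.c drops the per-visit breakdown that 7.a has. An analyst could follow either section and report a different number for the same primary outcome.

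Second, the denominator is fixed at screening, but the intervention starts at the Treatment visit. For the immediate group the gap is about a week. For the delayed group it is about 7 weeks, and it is there to serve secondary objective (c), the comparison with spontaneous change. Someone who leaves during that wait has not been given the manual, yet would be missing at all three counted visits. A single rate over everyone eligible then combines tolerance of a waiting period with engagement with the intervention, and only the second is what the primary objective asks about. The figure is meant to inform later trials, so its reading matters even in a descriptive pilot.

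**Working it through.** The documents state no engagement figure, so there is nothing to reproduce. The check compares the wording and then works through the arithmetic under labelled assumptions.

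**1. The two definitions.** Section 7.a: unit is the assessment, one figure per televisit. Section 7.c: unit is the televisit, no breakdown stated. Denominator in both: eligible participants. At a given visit the two agree only if every attender finishes every form. If 80% attend and 10% of forms are left undone (assumed), the results are 80% and 0.80 × 0.90 = 72%.

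Aggregating over visits opens a gap even with perfect form completion. By Table 1 a non-smoker has 2 participant-completed measures at Treatment, 13 at Week 7 and 12 at Week 14, which is 27 in all. With assumed attendance of 90%, 80% and 70%:
- televisits: (90 + 80 + 70)/3 = 80.0%
- assessments: (0.9 × 2 + 0.8 × 13 + 0.7 × 12)/27 = 20.6/27 = 76.3%

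**2. Effect of the wait.** Let w_imm and w_del be the proportions lost between eligibility and the Treatment visit in each group, and r the Week 7 completion among those who had the Treatment visit. With an assumed 1:1 split:
- overall Treatment rate = 0.5(1 − w_imm) + 0.5(1 − w_del)
- overall Week 7 rate = overall Treatment rate × r
- fall in the Treatment rate due to the longer wait = 0.5(w_del − w_imm)

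So each 10 points of excess loss costs 0.5 × 10 = 5 points. With w_imm = 5% and r = 90% (both assumed):

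| w_del | Overall Treatment | Overall Week 7 | Week 7 ÷ Treatment |
|---|---|---|---|
| 5% | 95.0% | 85.50% | 90% |
| 10% | 92.5% | 83.25% | 90% |
| 20% | 87.5% | 78.75% | 90% |
| 30% | 82.5% | 74.25% | 90% |
| 40% | 77.5% | 69.75% | 90% |

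Completion among the treated is 90% in every row, while the all-eligible Week 7 figure moves by 15.75 points. The last column shows that the ratio of the two per-visit figures recovers the 90%, provided nobody misses Treatment and returns later. What cannot be recovered without a split by group is why people missed the Treatment visit.

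**3. Precision.** Wilson 95% intervals at an assumed 80% completion: 80/100 gives 71.1% to 86.7%, a half-width of (86.7 − 71.1)/2 = 7.8 points. 40/50 gives 67.0% to 88.8%, a half-width of (88.8 − 67.0)/2 = 10.9 points.

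**The case against.** The strongest reply is that the plan already does most of what is needed. Section 7.a reports by visit, and Week 7 divided by Treatment approximates completion among those treated without any split by group. This stands if 7.a is followed. It does not explain non-attendance at Treatment, and 7.c omits the per-visit wording.

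Retention of everyone eligible is also a proper feasibility measure for a pilot. That stands too, and is a reason to keep the figure under its own name. Conditioning on attending Treatment selects the more motivated and can overstate engagement, so that figure should be supportive only.

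Assessments are collected at staff-run televisits, so a large gap between forms and attendance at one visit is not to be expected. The 80% against 72% example shows that the definitions can differ, not that they will by that much.

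A reader might infer more than the documents support:
- That the plan commits to pooling over arms. It names one denominator and no split, so pooling is an inference.
- That half the sample waits. Urn randomisation is described without a ratio.
- That wait losses certainly count as non-completion. This follows from the denominator as worded, but the handling of removed participants is not stated.
- That the whole primary outcome is affected. The acceptability items are asked at the Week 7 visit, 7 weeks after Treatment, so people lost in the wait never enter them.
- That leaving the six weekly surveys out of the primary outcome is an error. They measure outcomes and are not part of the intervention as section 4.h defines it, so omitting them is a legitimate choice.

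**Conclusion.** The point holds for the attendance component. It has two wordings, and, followed as written, either one mixes loss before the intervention with engagement with it. The likely direction is understatement, if the 7-week wait loses more people than the immediate group's gap of about a week. The size cannot be determined from the documents: under the assumed 1:1 split it is half the excess wait loss. All loss rates used here are illustrative. The plan is mainly descriptive and has no engagement threshold, so no stated decision turns on the figure. This is an inexpensive improvement that lets the primary figure answer its own question, not a flaw that invalidates the outcome.

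**What to change.** Use one definition in both 7.a and 7.c: televisit attended, given separately for Treatment, Week 7 and Week 14. Report it by randomised group with 95% confidence intervals, and say whether participants removed under section 4.g stay in the denominator. Keep the figure over all eligible participants, labelled as trial retention. Read the immediate group as the main estimate of engagement with the intervention. Give Week 7 and Week 14 completion among those who had the Treatment visit as supportive, noting that it is conditional on attending that visit.

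This changes wording only and uses data already being collected, with no new visits or participants. The cost is precision: about ±11 points per group at an assumed 50 per group, against about ±8 points for all 100.

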
credentialed Qualtrics links provided to them by the study staff. Our study staff is experienced in implementing Qualtrics surveys remotely in prior studies and has extensive experience providing brief intervention for caffeine reduction using the manual-only approach. These data will support feasibility and initial efficacy of future randomized controlled trials in populations experiencing specific caffeine-related problems.

2. Objectives (include all primary and secondary objectives)

Primary objective. Determine to what extent participants will engage with a remote caffeine reduction intervention for caffeine-related problems and find it acceptable.

Secondary objective (a). Determine to what extent participants are successfully able to reduce their caffeine consumption following the remote intervention.

Secondary objective (b). Determine to what extent participants report improvement in common caffeine-related problems (e.g., insomnia, anxiety, gastrointestinal distress) following the remote intervention.

Secondary objective (c). Determine whether participants randomized to the immediate intervention group (at 7-weeks post enrollment and post-treatment) show greater caffeine reductions or greater improvements in caffeine-related problems relative to the delayed treatment group at 7-weeks post-enrollment (prior to delayed treatment). This randomization will allow us to compare the initial efficacy of our intervention with caffeine reductions that may occur spontaneously over the same duration.

3. Background (briefly describe pre-clinical and clinical data, current experience with procedures, drug or device, and any other relevant information to justify the research)

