Week 7 Follow-up Televisit. At approximately 7 weeks after the treatment televisit, participants will complete a follow-up televisit at which they will complete the same measures as previously administered to assess anxiety, depressed mood, sleep problems, gastrointestinal problems, past week caffeine/cigarette use, and caffeine-related problems as outlined in Table 1. Participants will also complete a treatment acceptability survey.

Week 14 Follow-up Televisit. Finally, participants will complete a follow-up visit approximately 14 weeks after the treatment televisit. They will complete all the same assessments as the Week 7 televisit, except they will not repeat the treatment acceptability survey.

Table 1. Study measures according to visit

	Preliminary Online Screening	Screening Televisit	Treatment Televisit	Weekly Surveys (Weeks 1-6)	Week 7 Televisit	Week 14 Televisit
Basic screening questions/demographics ¹	X					
Typical Week Caffeine Survey	X					
AUDIT-C ²	X					
DAST-10 ³	X					
PROMIS-Anxiety-8a ⁴	X			X	X	X
PROMIS-SleepDisturbance-8a ⁴	X			X	X	X
PROMIS-GIDiarrhea-6a ⁴	X			X	X	X
PROMIS-GIReflux-13a1.0 ⁴	X			X	X	X
PROMIS-Depression-8a ⁴	X			X	X	X
Consent Quiz ¹		X				
Medical History Survey ¹		X				
Drug Use History Matrix ¹		X				
Caffeine Timeline Follow-back ¹		X	X		X	X
Past 7 Days Caffeine Survey ¹		X	X	X	X	X
Past 7 Days Cigarette Survey (smokers only) ¹		X	X	X	X	X
Caffeine Problems Survey ¹		X				
Caffeine Use Disorder Questionnaire ¹		X			X	X
Caffeine Use Disorder Interview ¹		X				
GAD-7 ⁵		X			X	X
PSQ-I ⁶		X			X	X
Insomnia Severity Index ⁷		X			X	X
GSRS ⁸		X			X	X
Treatment Acceptability Survey/Interview ¹					X	
Observer Rating Survey (Completed by Community Observer) ¹				X		X

Note. Detailed descriptions of all measures are appended to the present IRB application in the "Measures" document. ¹Study team-generated measure/survey based on prior research (e.g., Sweeney et al. 2019, 2020). ²Alcohol Use Disorders Identification Test-C, Bush et al., 1998. ³Drug Abuse Screening Test, Skinner 1982. ⁴Patient-Reported Outcomes Measurement Information System, Cella et al., 2010, Rothrock et al., 2010. ⁵Generalized Anxiety Disorder-7, Spitzer et al., 2006. ⁶Pittsburgh Sleep Quality Index, Buysse et al., 1989. ⁷Bastien et al., 2001. ⁸Gastrointestinal Symptom Rating Scale, Svedlund et al., 1988.

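### Objective (c) needs a symptom score from the delayed group just before it gets the manual, and none is scheduled; for caffeine intake the score exists, but 7c names no time origin or contrast

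*Combined protocol and SAP*

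**What the plan says.** Section 2, secondary objective (c), sets the immediate group, after treatment, "relative to the delayed treatment group at 7-weeks post-enrollment (prior to delayed treatment"). Section 7b repeats the comparison "at the 7-week follow-up relative to the delayed treatment group over the same time-period" and applies it to every secondary outcome, so to symptoms as well as caffeine intake. For objective (b), section 7b also uses symptom scores from the treatment televisit as a comparator. Section 7c says that means and SDs of the Table 1 assessments "will be calculated for screening, treatment, 7 Week Follow-Up and 14-Week Follow-Up visits".

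On timing, section 4a has the delayed group's Treatment "visit scheduled for a date approximately 7 weeks after screening". The later visits are counted from treatment in both groups: "At approximately 7 weeks after the treatment televisit, participants will complete a follow-up televisit", and "participants will complete a follow-up visit approximately 14 weeks after the treatment televisit".

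On measures, the section 4a description of the Treatment televisit mentions only caffeine and cigarette use, and Table 1 agrees. The first weekly survey, which carries the symptom scales, is requested seven days after that visit.

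On analysis, section 7c gives "a mixed effects regression model with between-subjects factors of group, a within subjects factor of time, and a group x time interaction term" for the group comparison. It justifies N = 100 by a power calculation "with two groups, four measurements", alpha .05, power .95, correlation .5 and partial eta squared .02, and also by the laboratory's capacity.

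**The concern.** The waiting-list arm is there to separate the effect of the manual from change that would have happened anyway. That requires a value for the delayed group at the end of its wait and before it receives the manual. If the value is not collected, no later choice of analysis can supply it. If it is collected but the analysis does not say how it is used, the contrast can be chosen after the data are seen, and one possible choice tests something else. This is the only inferential analysis of the randomised comparison in the plan.

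**Working it through.** **1. When each group is seen.** Approximate weeks from screening, from the timings in section 4a:

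| Group | Screening | Treatment | Week 7 | Week 14 |
|---|---|---|---|---|
| Immediate | 0 | 0–1 | 7–8 | 14–15 |
| Delayed | 0 | 7 | 14 | 21 |

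The comparison in objective (c) is therefore immediate group at Week 7 against delayed group at Treatment.

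**2. What is measured then.** In Table 1:
- The caffeine timeline follow-back and the past-7-days caffeine survey are marked at Screening, Treatment, Week 7 and Week 14. Intake is covered.
- GAD-7, PSQ-I, Insomnia Severity Index, GSRS and the Caffeine Use Disorder Questionnaire are marked at Screening, Week 7 and Week 14.
- The PROMIS scales are marked at preliminary screening, weekly in weeks 1–6, Week 7 and Week 14.
- The Caffeine Problems Survey is marked at Screening only.

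No symptom or caffeine-problem measure is marked at Treatment. The delayed group's first symptom score after screening comes at about week 7 + 1 = 8, seven days after the manual.

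**3. The plan's power figure.** Section 7c gives inputs but no formula. The usual one for a repeated-measures interaction has noncentrality λ = f²·N·m/(1−ρ), with f² = .02/.98 = .0204. With N = 100, m = 4 and ρ = .5, λ = .0204 × 100 × 4/.5 = 16.33 on 3 and 294 df, and power is .936 (.957 if f is rounded to .15). The stated .95 is thus roughly reproduced, for a four-measurement interaction. The same formula gives .885 for three measurements and .808 for two.

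**4. Intake, if time were coded by visit.** Assume 50 per group, correlation .5, no dropout, an effect of d SD equal in both groups, and spontaneous change of s SD over the 7-week wait. The means over the four visits are:
- immediate: 0, 0, −s−d, −s−d
- delayed: 0, −s, −s−d, −s−d

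The group differences are (0, s, 0, 0), and d has gone. With λ = N·Σ(D − mean D)²/[4(1−ρ)], λ = 100 × .75s²/2 = 37.5s². The omnibus test then rejects as follows, for any d:

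| Drift s (assumed) | 0 | 0.1 | 0.2 | 0.3 | 0.4 |
|---|---|---|---|---|---|
| λ | 0 | .375 | 1.5 | 3.375 | 6.0 |
| Rejection | .05 | .07 | .15 | .30 | .51 |

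Simulation agrees (10,000 trials per cell). The named contrast behaves differently: immediate at Week 7 minus delayed at Treatment is (−s−d) − (−s) = −d. It is a linear combination of cell means in the same model. Categorical time from enrolment (0, 7, 14 weeks) also keeps the effect in the omnibus test, with power .84 at d = 0.57.

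**5. Power of the named contrast.** The plan gives no difference in SD units. Reading partial eta squared .02 as a two-measurement interaction gives 25d² = 8.16, so d = 0.57. The noncentrality is d√25/√[2(1−ρ)] = 2.86 for a change score and d√25/√(1−ρ²) = 3.30 with baseline adjustment. Power is .81 and .90. Other readings of the same .02 give d = 0.61 (.85 and .93) or 0.66 (.90 and .965). With 80 completers (20% dropout, assumed), 0.57 SD gives .71 and .83.

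**The case against.** The plan never says that time is coded by visit. Objective (c) and section 7b already fix the comparison at 7 weeks from enrolment, and section 7c can be read in that light. It specifies a model, not an omnibus F test, and an analyst following 7b could extract the right contrast for intake. All of this stands, and it reduces the intake part to missing detail.

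A reader might infer that the four measurements in the power statement must be the four visits because the groups share no other four times. That does not follow. Caffeine intake is also surveyed weekly, and if the immediate group is treated about a week after screening, its Week 6 survey and Week 7 visit fall close to the delayed group's Treatment visit and first weekly survey. Exact cancellation also needs equal effects in the two groups.

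On symptoms, one can argue that sections 7b and 7c show an intention to score them at Treatment, that Table 1 may be at fault (its observer-rating row does not match the timing in section 4a), and that the appended Measures document, not seen here, may settle it. The contradiction remains, however: the section 4a text independently supports Table 1. The delayed group's first weekly survey is a near substitute for the PROMIS scales only, and it comes after the manual.

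**Conclusion.** The concern holds in two parts of unequal weight. The firm part is the symptom gap. On the schedule in section 4a and Table 1, the delayed group has no pre-manual 7-week score for anxiety, sleep, gastrointestinal or caffeine-problem measures, so that half of objective (c) cannot be answered. This rests on no assumption about coding or effect size.

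The lesser part is that section 7c leaves the time origin and contrast open for caffeine intake. A reader might conclude that the planned model cannot detect the treatment effect. The documents do not support that: the loss arises only under visit coding combined with the omnibus test, neither of which is stated, and the intake data needed are collected. Nor is the .95 a miscalculation. It is about right for a four-measurement interaction, but it is not the power of the 7-week contrast, which cannot be fixed without a difference in SD units. The power figures for that contrast depend on assumed differences, equal allocation and, except where dropout is shown, complete data.

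The point should be fixed, but the stakes are limited. Objective (c) is secondary, the analysis is mainly descriptive, means and SDs by visit will still be reported, and the feasibility outcomes are unaffected.

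**What to change.** 1. Reconcile sections 7b and 7c with section 4a and Table 1. Either give the existing online symptom measures at the Treatment televisit before the manual is provided, or limit objective (c) to caffeine intake. The first lengthens a visit expected to take under 30 minutes: the weekly survey takes about 5–10 minutes, and GAD-7, PSQ-I, Insomnia Severity Index and GSRS would add time the documents do not give. The second costs nothing in data collection but gives up the randomised symptom comparison.

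2. In section 7c, define time from enrolment for objective (c) and name the contrast: immediate group at the Week 7 follow-up against delayed group at the Treatment televisit before the manual, accounting for the screening value. A change score is valid; baseline adjustment has more power at correlation .5. Keep later visits for objectives (a) and (b). For intake this is wording only.

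3. State that the .95 refers to a four-measurement interaction. If power is claimed for the 7-week contrast, give the assumed difference in SD units and the dropout allowance.

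### The 7-week between-group comparison of caffeine intake does not condition on screening intake, so it is modestly less precise than the planned data allow

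*Combined protocol and SAP*

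**What the plan says.** Section 2, objective (c), compares the immediate group, after its treatment, with the other arm: "relative to the delayed treatment group at 7-weeks post-enrollment (prior to delayed treatment"). The stated purpose is to separate the intervention from spontaneous caffeine reduction.

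Section 4a (Screening Televisit) randomizes participants "using an urn randomization procedure accounting for caffeine consumption, age, and sex". Section 4a (Treatment Televisit) has the delayed group's Treatment "visit scheduled for a date approximately 7 weeks after screening" and adds: "Participants will also complete assessments to determine their caffeine consumption and cigarette use over the past 7 days as outlined in Table 1". Table 1 lists the "Past 7 Days Caffeine Survey" at the Screening, Treatment and Week 7 televisits, so a baseline and a 7-week value are planned in both arms.

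The only between-group model, in section 7c, is "a mixed effects regression model with between-subjects factors of group, a within subjects factor of time, and a group x time interaction term". It has no covariate and no constraint that the groups share a mean at screening, and the levels and origin of the time factor are not defined. The same section's power statement uses a correlation of .5 among repeated measures and "a desired power of .95". Effect sizes for future trials are to be calculated separately, "using means and standard deviations for pre-and post-treatment for all secondary outcomes".

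**The concern.** Screening caffeine intake is the baseline of the outcome, and caffeine consumption is a factor in the randomization, yet the analysis does not condition on it. Entering screening as a level of time does not do so. With unconstrained group means and complete data, the group x time contrast is simply the difference between groups in mean change. That estimate carries the full noise of the screening measurement, and its standard error takes no credit for the balance that the urn has already produced.

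What is at stake is precision: a wider interval and a slightly conservative test for the one randomized comparison of caffeine intake. Bias, false positives and the pre/post effect sizes for future trials are not affected. The point is limited to caffeine intake.

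**Working it through.** **Inputs.** From section 7c: N = 100, alpha .05, two groups, four measurements, correlation rho = .5, partial eta squared .02. Assumed, because the documents do not give them: 50 per group, a two-sided test, equal SDs at screening and 7 weeks (taken as 1), complete data unless stated, and the details of the urn.

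**1. The plan's sample size.** f² = .02/.98 = .0204. For a group x time interaction over four measurements, lambda = f² × N × 4/(1 - rho) = .0204 × 100 × 4/.5 = 16.33 on 3 and 294 degrees of freedom, which gives power .936. Power .95 at this f needs 108 participants; rounding f up from .143 to .15 gives 98. The figure of 100 is therefore approximately reproduced. It refers to a test across all four occasions, not to the 7-week contrast.

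**2. Variance of the 7-week contrast, closed form.**
- Difference in change: 2(1 - rho) × 2/50 = 1.00 × .04, SE .200.
- Conditional on screening intake: (1 - rho²) × 2/50 = .75 × .04, SE .173.
- Ratio: (1 - rho²)/(2(1 - rho)) = .65, .75 and .85 at rho = .3, .5 and .7.

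Fitted models on simulated data with four occasions agree: mean SE .199 for the planned interaction, .173 for regression on baseline, and .172 for a mixed model with equal screening means. At rho = .5 the change contrast is no more precise than comparing 7-week values alone, whose variance is also 1 × .04.

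**3. Allowing for the urn.** The ratio .75 overstates the true gain, because the urn already balances caffeine and so lowers the actual variance of the change contrast below what its model reports. Twelve urn rules were simulated (10,000 null trials each): pooled-urn, most-imbalanced-urn or stratum-urn draws; caffeine cut in 2 or 4; 0 or 1 starting balls. Age and sex had two levels each and were not prognostic.

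| rho = .5 | Planned contrast | With screening caffeine, age and sex |
|---|---|---|
| 95% half-width (SD) | .396-.397 | .346-.347 |
| Test size | .037-.044 | .048-.054 |
| Power at 0.571 SD | .807-.825 | .890-.901 |
| Power at 0.660 SD | .903-.923 | .958-.964 |

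True variance falls by 10.3-19.2% (11.1-20.3% with screening caffeine alone). Since 1/(1 - .103) = 1.115 and 1/(1 - .192) = 1.238, this is worth about 11-24 extra participants per 100. A separate simulation of eight rules (4,000 trials each) gave 13-20%, with planned test size .037-.046. Two further pooled-urn runs gave a planned size of .046-.048, so the conservatism is slight and depends on the rule.

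**4. Where the two differences come from.** The plan does not say how partial eta squared .02 translates into a 7-week difference. With two measurements, lambda = .0204 × 100 × 2/.5 = 8.16 and the difference is sqrt(8.16 × .04) = 0.571 SD. If the groups differ at one of four occasions, lambda = 100 × (1/4) × (3/4)/.5 × d² = 37.5 d², so d = sqrt(16.33/37.5) = 0.660 SD. Neither power is the plan's own.

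**5. Sensitivity of the true gain (all assumed settings).**
- rho .3: 16.4-28.4%; rho .7: 5.0-10.5%.
- 7-week SD 0.8 times the screening SD: 25.9-34.7%; 1.2 times: 5.5-9.0% (six rules, rho .5).
- Lognormal caffeine intake: 15.3-20.2% (six rules, rho .5).
- 15% of 7-week values missing completely at random: 9.1-17.8%, with no bias in either analysis (baseline-constrained against unconstrained likelihood, without age and sex).

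**The case against.** The strongest reply is that nothing here is an error. Group, time and group x time is a standard model, the estimate is unbiased, and section 7c presents the trial as a mainly descriptive pilot in which this comparison is secondary. All of that is true and limits the weight of the point. It does not remove it, because section 2 relies on the randomized comparison to rule out spontaneous change, and section 7c justifies the sample size by its ability to detect a treatment effect.

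Second, the figures presuppose that time runs from enrolment. If time were indexed by visit, the delayed group's Week 7 value would come after treatment, and the contrast would not address objective (c) at all. This stands, and it is why the time origin must be stated first.

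Third, most settings are assumed and were varied one at a time. For an SD ratio k, the closed-form variance ratio is k²(1 - rho²)/(1 + k² - 2 rho k). At rho .7 and k = 1.2 it is .734/.76, a gain of about 3% before any urn effect, which would reduce it further; at rho .3 and k = 0.8 the gain is about 50%. The range is therefore wider than the one-at-a-time figures show, though the closed-form gain stays positive.

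Fourth, the documents do not say which caffeine measure feeds the urn. Table 1 has a typical-week survey, a timeline follow-back and a past-7-days survey by the end of screening. If the urn uses a different measure from the outcome's baseline, the size of the gain and the test size would change, but the case for conditioning on baseline would not.

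Fifth, age and sex add nothing in the simulations because they were made non-prognostic, so the runs are no evidence on their value. Finally, the immediate group's Week 7 visit can fall about 8 weeks after screening, because its Treatment visit may be up to about a week after screening. Section 2 itself treats that visit as the 7-week point, but the difference should be acknowledged.

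**Conclusion.** The concern holds. The planned model leaves precision unused in the 7-week caffeine comparison. At rho = .5, with equal SDs and 100 participants, the true sampling variance could be 10-19% smaller and the reported interval about 13% narrower (0.346/0.397 = .87). The test's slight conservatism would be removed. The size rests on time being counted from enrolment, on the assumed urn rules and on the unknown correlation and SD ratio; it could be near zero in an unfavourable combination and well above 19% in a favourable one. The analysis is valid as planned, so this is a worthwhile improvement and not a correction of an invalid method.

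**What to change.** In section 7c, state that time is counted from enrolment for objective (c). Name the caffeine measure that serves as both baseline and outcome. Compare the value at the Week 7 televisit (immediate group) with that at the pre-treatment Treatment televisit (delayed group), noting the possible difference of about a week in timing.

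Use a mixed model with group means constrained equal at screening or, with complete data, a regression of the 7-week value on group and screening caffeine. Include age and sex (by time in the mixed model) because the urn uses them, without claiming a precision gain from them. Report the adjusted difference with its 95% confidence interval.

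The cost is a change of wording and up to three degrees of freedom. No new data are needed: screening caffeine, age and sex are known before randomization, and the 7-week values are already scheduled. The choice should be written down before the data are examined.
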